### **6.4 Tunneling Tool (Model MN15000)**

The tunneling tool is used to provide a conduit for the lead or lead extension to the IPG or away from the midline of the spine. It is packaged with two exchangeable tips (a blunt pencil tip and a sharp trocar tip), a straw, a hex key, and a torque wrench.

### **6.5 Trial Neurostimulator (MN10100)**

The external trial neurostimulator provides energy and controls electrical signals delivered to the leads. It has a belt clip and must be worn over a piece of clothing by the subject.

## Clinical Investigational Plan

### **6.6 DRG External Pulse Generator (EPG; 7599 & 7032)**

The DRG EPG functions in the same way as the MN10100 but is compatible with the same programming platform as the Proclaim DRG.

### **6.7 Implantable Neurostimulator Kit (MN10200)**

The implantable neurostimulator provides energy and controls electrical signals delivered to the leads. It is typically implanted by the physician in the abdomen or buttocks.

### **6.8 Proclaim DRG IPG, MR Conditional (Model 3664)**

The Proclaim DRG IPG was developed based on the FDA approved Proclaim SCS and Axium DRG pulse generators. It is a 16-channel, 4-port, non-rechargeable, MR Conditional IPG. The internal electronics, battery and external casing (can) are identical to the Proclaim SCSIPG used for SCS indications (Model 3660 and 3665). The Proclaim DRG uses the Axium header design (adapted for the Proclaim IPG cannister) which accommodates up to four DRG leads. Additionally, the firmware capability for Proclaim DRG was developed to match the capabilities of the Axium pulse generator. A pocket sizer is an accessory packaged with the IPG and is used to assess the implant size for the IPG. The Proclaim DRG pocket sizer is made of the same material used in the FDA approved Proclaim SCS pocket sizer, but with a different design to reflect the Proclaim DRG IPG shape and form.

### **6.9 Patient Programmer (MN10600-02)**

The patient programmer is set up under the instruction of the clinician or clinical staff to allow the subject to change the amplitude of the energy delivered by the implantable or trial neurostimulator system. The subject carries the programmer with them during daily use.

The patient programmer is powered by an internal rechargeable battery or it is plugged into a power outlet using the power supply cord provided. The patient programmer will be used by the subject to communicate with their implantable or trial neurostimulator system, to monitor the device, and to adjust the stimulation settings within their Investigator's prescribed limits. The subject is provided with a carrying case (MN13500) for carrying their patient programmer during their participation in this study.

The patient programmer has the following features:

- Turns OFF all stimulation
- Turns stimulation ON or OFF for each body region to be treated
- Adjusts stimulation amplitude for each lead in use
- Shows the subject's identification information
- Shows Investigator name and clinic name, along with contact information

The patient programmer contains an internal magnet to initiate communication with the implantable or trial neurostimulator system. The patient programmer is designed to be easy to use and establishes two-way communication with the implantable or trial neurostimulator system to control the stimulation delivered to the subject.

## Clinical Investigational Plan

### 6.10 Clinician Programmer (MN10700)

The clinician programmer is used by trained staff under the guidance of the clinician to communicate wirelessly with the implantable and/or trial neurostimulator system.

The clinician programmer has the following features:

- Turns OFF all stimulation
- Turns stimulation ON for up to four leads and measures lead impedance
- Allows the user to assign body regions that each individual lead is intended to stimulate, modify electrode configurations and adjust stimulation settings for each lead
- Creates multiple groups of stimulation settings for the subject
- Enters subject and lead identification information, Investigator and clinic name and contact information, and Investigator's notes
- Performs real time test stimulation to assess the subject's response for each lead
- Enables subject-controlled therapy and configures subject-controlled therapy settings for each lead
- Acquires identification, diagnostic, and historic information about the neurostimulator device
- Programs configured therapy settings for continuous stimulation

The clinician programmer contains an internal magnet to initiate communication with the implantable or trial neurostimulator device.

### 6.11 Clinician Programmer App [REDACTED]

The stimulation parameter ranges allowed by Clinician Programmer App (Model 3874 Version 3.3) are the same as the approved Axium system. The IPG stimulation settings are established via the Clinician Programmer (CP) App, which is installed on an off-the-shelf Apple iPad Mini. Different stimulation programs may be stored and selected via the Patient Controller (PC) App, which is installed on an off-the-shelf Apple iPod Touch. The clinician programmer communicates with the pulse generator via Bluetooth.

### 6.12 Patient Controller App [REDACTED]

The stimulation parameter ranges allowed by the patient controller App (Model 3875 Version 3.3) are the same as the approved Axium system. The IPG stimulation settings are established via the Clinician Programmer (CP) App, which is installed on an off-the-shelf Apple iPad Mini. Different stimulation programs may be stored and selected via the Patient Controller (PC) App, which is installed on an off-the-shelf Apple iPod Touch. The patient controller communicates with the pulse generator via Bluetooth.

## 7.0 SUBJECT SELECTION

Subjects who meet all of the inclusion criteria and none of the exclusion criteria are eligible to participate in this study. All subjects in the clinical study (including system trial failures, those withdrawn from the clinical study and those lost to follow-up) will be accounted for and documented by assigning an identification code linked to their [REDACTED], alternative identification or

## Clinical Investigational Plan

contact information. This log will be kept up to date throughout the clinical study by the principal investigator or his/her authorized designee.

### 7.1 Inclusion Criteria

To participate in this clinical study, the subject must meet all of the following inclusion criteria:

- Subject is male or female  $\geq 22$  and  $\leq 75$  years of age.
- Subject has moderate to severe chronic intractable pain of the lower limbs resulting from Complex Regional Pain Syndrome (CRPS) types I or II.
- Subject has a baseline VAS score of  $\geq 60$  mm for overall pain at the time of the baseline assessment.
- Subject is willing and able to comply with the study requirements.
- Subject is able to provide written informed consent.

### 7.2 Exclusion Criteria

Subjects are not eligible for this clinical study if they meet any of the following exclusion criteria:

- Subject has an active implantable medical device including but not limited to cardiac pacemakers and cardiac defibrillators.
- Subject is currently involved in medically-related litigation, including workers compensation.
- Subject has a life expectancy of less than one year.
- Subject is pregnant or of child bearing potential and not using adequate contraception as determined by the investigator.
- Subject has, or plans to have, a spinal cord stimulation system or infusion pump system implanted.
- Subject has, or plans to have, a peripheral nerve stimulation system (PNS) or peripheral nerve field stimulation system (PNfS) implanted.
- Subject is considered a poor surgical or study candidate, which may include, but is not limited to the following: any medical, social, or psychological problem that could complicate the implant procedure and/or recovery from the implant procedure or could complicate the required procedures and evaluations of the study in the judgment of the investigator.

## 8.0 METHODS AND PROCEDURES

### 8.1 Study Procedures

The clinical study will be conducted in accordance with the CIP. All parties participating in the conduct of the clinical study will be qualified by education, training, or experience to perform their tasks. The clinical study will not commence until St. Jude Medical receives written approval from the IRB and relevant regulatory authorities and all required documents have been collected from the site.

All required study procedures at each specified interval are outlined in the sections below. A table outlining the timing of all study activities by each visit is located at the end of this section.

## Clinical Investigational Plan

### 8.2 Informed Consent

### 8.3 Blinding

There is no blinding for the subject or the Investigator.

### 8.4 Subject Screening and Point of Enrollment

All subjects presenting at the investigational site will be screened by a member of the investigational team previously trained on the CIP and delegated to do so. After completion of the baseline visit, eligible subjects will be scheduled for the trial system implant. [REDACTED]

### 8.5 Baseline Visit

Baseline measurements for the subject's pain symptoms and location will be taken along with a brief treatment history and completion of subject self-reported questionnaires.

The following information will be collected at the baseline visit:

- Demographics
- Diagnosis
- Pain and treatment history
- VAS score
- NPS
- PROMIS-29 Profile domain scores
- PROMIS Global Health Scale score
- Protocol Deviations (if applicable)

### 8.6 Trial System Implant (approximately 30 days from Baseline Visit)

Subjects will use the trial system in accordance with the standard practice of the clinical site (typically 3-12 days). Trial system activation will occur in post-operative recovery after the implantation. At each visit, SJM field representatives may assist with programming of the subject's device under the supervision of the investigative team.

The following information will be collected at the trial system implant visit: [REDACTED]

### 8.7 End of System Trial Visit (length determined by the site's standard of care; typically 3-12 days after trial system implantation)

At the end of the system trial phase, subjects will complete their trial system evaluation prior to removal of the system components. Only subjects who report a 50% or greater reduction in overall pain intensity through direct patient-reported percentage of pain relief will be eligible to receive the permanent implant.. The subject will then be withdrawn from the study.

The following information will be collected at the end of the system trial visit:

- Programming parameters
- Length of trial (days)
- Pain relief (direct patient report of percentage of pain relief)
- Decision on whether to proceed to permanent implant
- Reason subject will not proceed to the permanent implant (if applicable)

## Clinical Investigational Plan

- AEs (if applicable)
- Protocol Deviations (if applicable)

### 8.8 Permanent System Implant (approximately 30 days from End of System Trial visit)

The permanent implant should occur approximately 30 days from the End of System Trial visit. The following information will be collected at the permanent system implant visit:

- Procedure information
- Device information
- AEs (if applicable)
- Protocol Deviations (if applicable)

### 8.9 Device Activation (timing determined by the site's standard of care; may occur at the time of permanent system implant)

Permanent system device activation will occur according to the site's standard of care and may occur at the time of the permanent system implant. At each visit, SJM field reps may assist with programming of the subject's device under the supervision of the investigative team.

The following information will be collected at the activation visit:

- AEs (if applicable)
- Protocol Deviations (if applicable)

### 8.10 Scheduled Follow-ups

Subjects will report to the office at [REDACTED] months after the activation visit. The following information will be collected at these visits:

- VAS score
- NPS
- PROMIS-29 Profile domain scores
- PROMIS Global Health Scale score
- PGIC score
- Change in occupational status
- Change in activity level
- Satisfaction with device/therapy
- Willingness to undergo the procedure again
- Willingness to recommend the procedure to someone
- Sensations generated by stimulation
- Programming parameters
- AEs (if applicable)
- Protocol Deviations (if applicable)

All information, including subject questionnaires, should be collected prior to reprogramming, if reprogramming is needed. Missed visits and visits that occur outside of the specified time windows will be documented as protocol deviations.

If a study participant is unable or unwilling to attend an in-person visit, the visit may be conducted remotely using telemedicine as provided by the study center. Questionnaires may be

## Clinical Investigational Plan

administered during the remote visit. The numeric rating scale (NRS) may be used to collect a subject's pain score in place of the visual analog scale. Both are valid measures of pain intensity and studies support a strong relationship between both . The Coordinator or designee must document the subject's responses on the worksheet, note that the responses were collected via phone, save that document as source data, and enter the information in the EDC system. Alternately, questionnaires may be mailed to the participant in a return postage provided envelope. If this method is chosen, the Coordinator or designee should schedule a call with the subject to clearly explain the questionnaires and answer any questions the subject may have.

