#### Visual Analog Scale (VAS) for Pain

The VAS is a common, self-administered measure in which subjects rate their pain intensity by marking a vertical line through a 100 mm horizontal line anchored by word descriptors on each end (no pain to worst imaginable pain). The distance between the beginning of the horizontal line and the vertical line is measured to produce a score between 0 and 100 mm (or 0 to 10 cm). A higher score indicates higher pain intensity and a 30% reduction in VAS score from baseline to follow-up is considered clinically relevant. VAS scores for overall pain intensity will be collected.

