#### Numeric Rating Scale for Pain (telemedicine visits)

The pain NRS consists of 1 question that will be asked by interviewing the subjects. Patients will be asked to rate, from 0 (no pain) to 10 (worst imaginable pain), their average pain over the past 24 hours specific to the area(s) of chronic pain being treated. A higher score indicates greater pain intensity

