### 10.2 Secondary Endpoints

#### 10.2.1 Reduction in pain intensity (VAS)

The endpoint will test whether subjects achieve a clinically relevant change (mean percentage reduction of at least 30%) in VAS score at 12 months from baseline. Percentage change in VAS score is calculated within each subject as:

$$\% \text{ Change in VAS score} = (\text{VAS at baseline} - \text{VAS at 12-month})/\text{VAS at baseline} * 100\%$$

The following hypothesis will be tested:

$$H_0: \text{Mean \% Change in VAS score} \leq 30\%$$

$$H_1: \text{Mean \% Change in VAS score} > 30\%$$

The hypothesis will be tested at the 5% significance level. The analysis will be carried out by calculating the 95% lower confidence bound (LCB) on the mean % Change in VAS from baseline to 12-month visit based on a t-distribution. If the 95% LCB is greater than 30.0%, the null hypothesis is rejected. The analysis population for this secondary endpoint will include subjects who complete both baseline and 12-month VAS scales, irrespective of IPG types.

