### 10.8 The Treatment of Missing, Unused, or Spurious Data, Including Drop-Outs and Withdrawals

Analyses of each endpoint will be performed in subjects who provide complete data for each endpoint. Subject accountability for enrolled subjects will be performed prior to analyses of the primary and secondary endpoints. There are no plans to perform imputations for missing data.

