2.3.2 Secondary Endpoints

2.3.3 Reduction in pain intensity (VAS)

The endpoint will test whether subjects achieve a clinically relevant change (mean percentage reduction of at least [REDACTED]) in VAS score at 12 months from baseline.

Percentage change in VAS score is calculated within each subject as:

$$\% \text{ Change in VAS score} = (\text{VAS at baseline} - \text{VAS at 12-month})/\text{VAS at baseline} * 100\%$$

The following hypothesis will be tested:

[REDACTED]

The hypothesis will be tested at the 5% significance level. The analysis will be carried out by calculating the 95% lower confidence bound (LCB) on the mean % Change in VAS from baseline to 12-month visit based on a t-distribution. If the 95% LCB is greater than [REDACTED], the null hypothesis is rejected. The analysis population of this secondary endpoint will include primary analysis population subjects who complete both baseline and 12-month VAS scales.

Statistical Analysis Plan

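### The NRS allowed in place of the VAS at remote visits is described as treated-area pain, while the baseline and endpoint VAS is described as overall pain.

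*Protocol*

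**What the plan says.** Protocol 8.10 opens a remote route for follow-up: "If a study participant is unable or unwilling to attend an in-person visit, the visit may be conducted remotely using telemedicine". It then states: "The numeric rating scale (NRS) may be used to collect a subject's pain score in place of the visual analog scale". Its support for the switch is that both scales are valid and strongly related. The same paragraph also allows questionnaires to be mailed, with a call to explain them.

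Protocol 8.13 describes the two instruments differently. The NRS is an interview question on a 0 to 10 scale about "their average pain over the past 24 hours specific to the area(s) of chronic pain being treated". For the VAS, the section says "VAS scores for overall pain intensity will be collected" and gives no recall period. Eligibility (7.1) requires a VAS of at least 60 "mm for overall pain at the time of the baseline assessment", and the secondary endpoint (4.4; SAP 1.4.2) is percent change in overall pain on the VAS.

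Protocol 10.2.1 tests whether mean percentage reduction exceeds 30%, in "subjects who complete both baseline and 12-month VAS scales". SAP 2.3.3 narrows this to "primary analysis population subjects who complete both baseline and 12-month VAS scales". Neither mentions the NRS. Protocol 10.8 adds: "There are no plans to perform imputations for missing data".

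**The concern.** The outcome is a within-subject percentage change, so the same question has to be asked at both ends. A strong relationship between scale formats supports moving from a line to a number. It does not cover a change in the body region the subject is asked to rate.

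The visible text leads to one of two results for a subject with only an NRS at month 12:

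- **Excluded.** This is the literal reading of 10.2.1, 10.8 and SAP 2.3.3. Remote visits exist for people who cannot or will not attend, so the loss may be related to outcome.
- **Pooled.** The substitution wording in 8.10 suggests this, as does 10.9, which states no intent to exclude information from hypothesis tests. A treated-area score is then subtracted from an overall-pain baseline.

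The VAS secondary endpoint is affected, as are the 1-, 3- and 6-month VAS summaries. So are the 30% and 50% responder percentages (10.4) if they use the same score.

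**Working it through.** The plan gives no figure to reproduce on this point. The mismatch rests on wording; the arithmetic only illustrates its possible size.

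**Wording side by side**

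| | Remote NRS (8.13) | VAS (7.1, 8.13, 4.4) |
|---|---|---|
| Region described | treated area(s) | overall pain |
| Recall | 24-hour average | not stated |
| Mode | interview | self-completed |
| Scale | 0-10 | 0-100 mm |

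Only the region row, among the features of the question itself, shows two stated and different descriptions. For recall, a stated window faces an unstated one.

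**Inputs from the documents:** 287 subjects at month 12 (Section 5.0, set for the SAE analysis and borrowed here); eligible baseline 60-100 mm (7.1, 8.13); threshold 30% with a one-sided 95% bound (10.2.1).

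**Assumed inputs:** share f of NRS-only subjects at month 12, 10% to 30%; SD of percentage change, 35 points; gap between treated-area and overall pain, 5 to 10 mm in either direction; outcome difference between excluded and retained subjects, 10 points in either direction.

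**If NRS-only subjects are excluded**
- n = 287 x (1 - f): 287 x 0.9 = 258; 287 x 0.7 = 201.
- Margin from mean to lower bound = t(0.95, n-1) x 35/sqrt(n): 3.41 at 287, 3.60 at 258, 4.08 at 201.
- Shift in the mean = f x 10: 1.0 to 3.0 points.

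**If they are pooled as NRS x10**
- Shift in mean percentage change = f x gap/baseline x 100.
- At 80 mm: 0.1 x 5/80 = 0.6 points; 0.3 x 10/80 = 3.75 points.
- Over 60-100 mm: from 0.1 x 5/100 = 0.5 to 0.3 x 10/60 = 5.0 points.

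**Could this reverse the test?** At n = 287 the test passes when the observed mean exceeds 30 + 3.41 = 33.41%. A shift of 3.75 points changes the decision only if the unshifted mean lies between 33.41 - 3.75 = 29.7% and 33.41 + 3.75 = 37.2%. For a 5.0-point shift the band is 28.4% to 38.4%. With SD 25 or 45 the 3.75-point band is 28.7-36.2% or 30.6-38.1%.

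As a rough guide to where the mean may fall, Section 2.0 reports 74.2% 12-month success in the earlier trial, success requiring at least a 50% reduction. If that carried over and everyone else averaged no change, the mean would be at least 0.742 x 50 = 37.1%. That is a floor near the top of these bands, since successes count at exactly 50%. It is indicative only, because that trial scored the area of greatest pain.

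**The case against.** The strongest reply is that the difference may be verbal. The protocol does not reproduce the VAS question, the forms are held under separate cover (Appendix F), and overall pain is nowhere defined as whole-body pain. In subjects enrolled for lower-limb CRPS pain, it could mean overall pain from that condition. This stands as a limit: what is documented is a mismatch between two protocol descriptions. It is still a reason to align them.

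Second, NRS use is optional and questionnaires may be mailed, so a paper VAS may be obtainable without an office visit. This also stands. It may reduce the number of NRS-only subjects, and it supplies part of the remedy.

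Third, a handling rule may sit in redacted SAP sections (2.1.1, 2.9, 2.13, 3.5.2, 4.1.1). A reader might infer that no rule exists; the documents do not support that. But an analysis rule cannot change the question the NRS asks.

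Two other stronger readings should be resisted. One is that the recall periods conflict: the VAS period is not readable, so this cannot be said. The other is that the 5% error rate is badly inflated. If the true mean were exactly 30%, with baseline 75 mm, 25% NRS scores and treated-area pain always 10 mm lower, the rejection probability would be about 41-59% for SD 40 to 30. Every one of those conditions is assumed, and the effect reverses if treated-area pain is scored higher.

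**Conclusion.** The concern holds as a mismatch in the described body region between the remote NRS and the VAS it may replace. Depending on how NRS-only subjects are handled, the result is either a possibly selective loss from the 30% test or a percentage change built from two different questions.

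Size and direction are unknown, because the NRS-only share, the gap and the SD are not in the documents. Under the assumptions above, exclusion costs 0.2 to 0.7 points of precision and moves the mean by 1 to 3 points, while pooling moves it by 0.5 to 5.0 points. A reversed test is unlikely but not ruled out at the extreme inputs. A biased estimate is the more realistic consequence. The primary SAE endpoint is untouched. This should be corrected, but it does not threaten the study's main conclusion.

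**What to change.** 1. **Protocol 8.13 and 8.10.** Reword the remote NRS to ask about overall pain, with the same recall wording as the VAS form. At a remote month-12 visit, seek a mailed paper VAS first, using the route 8.10 already allows.
2. **Protocol 10.2.1 and SAP 2.3.3.** Keep the analysis of subjects with VAS at both times as the test that decides the 30% hypothesis, which is the current literal rule. Add one sensitivity analysis that includes month-12 NRS scores multiplied by 10. Flag scores collected under the treated-area wording and show the result with and without them. If a redacted section already holds a rule, cross-reference it.
3. **Supporting check.** Report the change in the PROMIS-29 0-10 pain intensity item, already a descriptive endpoint through month 12 (10.3), separately for NRS-only subjects. It uses the same item at both times, but it is a different instrument and supports the VAS result without replacing it.

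The cost is a small amendment with IRB notification or approval as Section 15.0 requires, a revised remote worksheet, two NRS wordings within one study, and one extra analysis. The PROMIS-29 breakdown needs no new data collection.
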